4.6 Volume of blood sampling

The total volume of blood that will be drawn from each subject in this study is as follows:

Table 5 Volume of blood to be drawn from each subject

Assessment	Sample volume (mL)	No. of samples	Total volume (mL)
PK samples	2	42	84
Genetic sample	9	1	9
ADP induced platelet aggregation	4.5	30	135
HIV, HBsAg, hepatitis C	10	1	10
Clinical chemistry	10	8	80
Hematology	9.5	8	76
Limited chemistry panel	10	3	30
Serum pregnancy test	1	2	2
Total			426

4.7 Adverse events

The definitions of adverse events (AEs), serious adverse events (SAEs) and other significant adverse events (OAEs) and the recording of AEs are given in Appendix B. It is of the utmost importance that all staff involved in the study are familiar with the content of these sections. The principal investigator is responsible for ensuring this.

4.7.1 Recording of adverse events

The subjects will be told to report any AE occurring during the study to the investigator or his personnel. Open, standardized AE questioning such as “Have you had any health problems since the previous visit?” will be done by the investigators or their personnel at each contact with the subject. The AE open, standardized questioning should be done discretely in order to prevent the subjects from influencing each other.

Information about AEs will be collected from the first administration of study drug until the completion of the follow-up visit (Visit 5). Serious adverse event information will be collected from the time the subject signs the informed consent until the follow-up visit. Any AEs observed or reported by a subject and/or staff will be recorded in the CRF. Any AE

including clinical findings not resolved on the final dosing day will be followed until resolved or explained.

Laboratory and vital signs abnormalities will not be recorded as an AE unless any criterion for an SAE is fulfilled, the subject discontinues the study due to the result(s), or the investigator considers it to be of such clinical importance as to merit recording it as an AE. If a laboratory value or vital sign is associated with clinical signs or symptoms, the signs or symptoms should be reported as an AE and the associated laboratory value or vital sign should be considered additional information. Any sign or symptom that fulfills SAE definition (Appendix B) or are the reason for discontinuation of study drug should be reported accordingly (refer to Section 4.7.2).

To avoid colloquial expressions, the AE term should be reported in standard medical terminology when possible. For each AE, the investigator will evaluate and report the onset (date and time), resolution (date and time), intensity, causality, action taken, serious outcome (if applicable) and whether or not it caused the subject to discontinue the study.

The following variables will be recorded for each AE:

Onset, resolution, maximum intensity, action taken, outcome, causality (yes or no) and whether it constitutes an SAE or not.

The intensity rating is defined as:

1 = mild (awareness of sign or symptom, but easily tolerated)

2 = moderate (discomfort sufficient to cause interference with normal activities)

3 = severe (incapacitating, with inability to perform normal activities)

It is important to distinguish between serious and severe AEs. Severity is a measure of intensity whereas seriousness is defined by the criteria in Appendix B. An AE of severe intensity need not necessarily be considered serious. For example, nausea, which persists for several hours, may be considered severe nausea, but not a SAE. On the other hand, a stroke, which results in, only a limited degree of disability may be considered a mild stroke but would be a SAE.

AEs will be classified using the most current version of the Medical Dictionary for Regulatory Activities (MedDRA). Coding of AEs will be made in the Astra Monitoring System (AMOS).

4.7.2 Reporting of serious adverse events

When the investigator becomes aware of an SAE during the course of the study, the SAE must be reported to the local monitor or other AstraZeneca representative within one (1) day.

All SAEs have to be reported, whether or not considered causally related to the investigational product. All SAEs will be recorded in the case report form. The investigator is responsible

for informing the Ethics Committee and/or the Regulatory Authority of the SAE as per local requirements.

The AstraZeneca representative will work with the investigator to compile all the necessary information to ensure that the appropriate AstraZeneca Drug Safety Department receives a report within one day for all fatal and life-threatening cases and within five days for all other SAEs. Follow-up information on SAEs should also be reported by the investigator in the same time frames. If a non-serious AE becomes serious, this and other relevant follow-up information must also be provided to AstraZeneca within 1 day as described above.

The following procedure must be followed in the case of a serious adverse event. The same contact information is to be used in case of medical emergency.

YOU MUST REPORT ANY SERIOUS ADVERSE EVENT, INCLUDING DEATH DUE TO ANY CAUSE, IMMEDIATELY. COMPLETE THE ASTRAZENECA SERIOUS ADVERSE EVENT REPORT FORM AND CONTACT ONE OF THE PEOPLE LISTED IN THE ASTRAZENECA EMERGENCY CONTACT PROCEDURE ON PAGE 2 OF THIS PROTOCOL.

YOU MUST FOLLOW ALL SUBJECTS WITH A SERIOUS ADVERSE EVENT, INCLUDING DISCONTINUED SUBJECTS, UNTIL RESOLUTION OF THE ADVERSE EVENT.

5. STUDY MANAGEMENT

5.1 Monitoring

5.1.1 Study monitoring

The monitoring of this study will be performed in accordance with the principles of Good Clinical Practice (GCP) as laid out in the International Conference on Harmonization (ICH) document “Good Clinical Practice: Consolidated Guideline”.

5.1.2 Data verification

It is a prerequisite of this study that the study monitor has direct access to source data for data verification. This will be done by comparing data from the CRFs with those in the subject’s medical notes (permission from the subject will be sought as part of the consent process). Such verification is an essential element of quality control, as it allows the rectification of transcription errors and omissions.

Monitoring will routinely be performed prior to the transfer of data to Data Management.

5.1.3 Direct access to source data

The monitor(s) will verify data from the CRFs against source data before collecting the CRFs to ensure accuracy and completeness of documentation, and to ensure that the principal investigator has submitted the CRFs to AstraZeneca.

5.2 Archiving of study documentation

AstraZeneca will retain all documentation pertaining to this study in the AstraZeneca central files for as long as AZD6140 is available for human consumption.

The investigator will retain all documentation pertaining to this study for at least 15 years.

5.3 Audits and inspections

Authorized representatives of AstraZeneca, a regulatory authority, an Independent Ethics Committee (IEC) or an Institutional Review Board (IRB) may visit the center to perform audits or inspections, including source data verification. The purpose of an AstraZeneca audit or inspection is to systematically and independently examine all study related activities and documents to determine whether these activities were conducted, and data were recorded, analyzed, and accurately reported according to the protocol, GCP guidelines of the ICH and any applicable regulatory requirements. The investigator should contact AstraZeneca immediately if contacted by a regulatory agency about an inspection at his or her center.

5.4 Training of staff

The principal investigator will maintain a record of all individuals involved in the study (medical, nursing and other staff). He or she will ensure that appropriate training relevant to the study is given to all of these staff, and that any new information of relevance to the performance of this study is forwarded to the staff involved.

5.5 Changes to the protocol

Study procedures will not be changed without the mutual agreement of the principal investigator and AstraZeneca.

If it is necessary for the study protocol to be amended, the amendment and/or a new version of the study protocol (Amended Protocol) must be notified to or approved by each IEC or IRB, and, if applicable, also the local regulatory authority, before implementation. Local requirements must be followed.

If a protocol amendment requires a change to a particular center's Written Informed Consent Form, then AstraZeneca and the center's IEC or IRB must be notified. Approval of the revised Written Informed Consent Form by AstraZeneca and by the IEC or IRB is required before the revised form is used.

AstraZeneca will distribute amendments and new versions of the protocol to the principal investigator who in turn is responsible for the distribution of these documents to his or her

IEC or IRB, and to the staff at his or her center. The distribution of these documents to the regulatory authority will be handled according to local practice.

5.6 Study agreements

The principal investigator must comply with all the terms, conditions, and obligations of the study agreement for this study. In the event of any inconsistency between this protocol and the clinical study agreement, this protocol shall prevail.

5.7 Study timetable and termination

The study is expected to start _____, and to be completed by _____.

Discontinuation or suspension of the whole study program

If AstraZeneca decides to withdraw or suspend the study, the investigator, the head of the institution and regulatory authorities should be informed of the fact in a written form clarifying the reason.

The principal investigator will immediately notify the decision to the subjects, give appropriate medical treatment, take necessary measures, and record treatment or measures provided on the source documents.

Completion of the study

Upon terminating the study, the principal investigator will report in writing the completion of the study as well as a summary of the results to the head of the institution in accordance with the institution's rules. The head of the institution will then notify, in writing, the IRB and AstraZeneca and will also provide a summary of the results to both parties.

5.8 Data management

5.8.1 Case report forms

CRFs will be provided for the recording of data. The CRFs will be in triplicate with carbonless paper. Data should be recorded directly and legibly from the source documents onto the CRFs, preferably in black ballpoint pen. Corrections to the CRFs should be made legibly, initialed and dated. Correction fluid or covering labels must not be used. The top original (white) and the first copy (yellow) of each completed CRF will be collected and returned to the AstraZeneca designee; the investigator will retain the second copy (manila).

AstraZeneca Data Management will enter the CRF data on an ongoing basis into their standard commercial database. The data will be verified and cleaned with electronic edit checks comprised of validated computer programs and manual data review. Any missing, inconsistent or illegible entries into the CRFs will be referred back to the investigator via the site monitor using Data Query Forms within an agreed number of days upon entering the data. Responses should be received by Data Management and updated within an agreed number of days upon generating the data queries. Clean file will be declared when all of the following have been completed: all data have been accounted for and have been databased; all edit

checks have been run and data discrepancies have been resolved or accepted; all serious adverse events have been reconciled with the clinical database; all coding is complete and has been medically reviewed and approved; and quality control of the database against the CRFs and relevant data sources has been completed.

5.8.2 Pharmacogenetic data

The genotype data will be used to explore genetic factors in the disposition of and response to AZD6140. The results of the genetic study will not form part of the clinical study database or the clinical study report. The results of this study may be pooled with genetic results from other studies on AZD6140 to generate hypotheses to be tested in future studies.

The DNA sample will not be labeled with the subject's name but will only be identified by a code that will link it to other information collected about the study drug during the course of this study. This link will exist to provide a way for regulatory authorities to track and ensure clinical genetic research is being conducted correctly and will be maintained only for the period of time that these authorities require; it will be destroyed after 15 years. If the subject changes his/her mind about this testing after donating a blood sample, this link will be used to track and destroy the sample. The study sponsor can only guarantee the possibility of destroying the sample while the link is maintained.

Test results will be kept confidential in accordance with all applicable laws. None of the test results will be provided to the subject, any insurance company, the subject's employer or family, the investigator or any other physician who is treating the subject or may treat the subject in the future.

The subject's DNA will not be used for any purpose other than genotyping. DNA will not be passed on to any other party and all samples will be retained for a 15-year period.

6. STATISTICAL METHODS AND DETERMINATION OF SAMPLE SIZE

6.1 Statistical evaluation

Statistical analysis will be carried out by Biostatistics at AstraZeneca, Wilmington, Delaware using SAS (version 8). Summary graphics required for presentation in the text portion of the Clinical Study Report (CSR) will be done using Sigmaplot 2000. Other graphics intended for use as supplemental figures and individual profile figures will be done using SAS. A comprehensive Statistical Analysis Plan (SAP) will be prepared and finalized before unblinding and analysis of the data.

The goal of the PK analysis is to estimate the effect of ethnicity (Japanese vs. Caucasian) on exposure to AZD6140 and AR-C124910XX over the current dose range of AZD6140. Therefore, no formal hypothesis testing will be performed, though estimation of the ratio of exposure (Japanese/Caucasian) will be supported with two-sided 90% confidence intervals (CI). The analysis of pharmacokinetics will involve subjects included in the primary analysis

set. Estimation of the effect of ethnicity will be performed at each dose level in the study. Graphical methods will be widely used in support of estimation of effects and summary statistics where indicated below. Differences in gender will be addressed descriptively by comparing the PK parameters across gender within an ethnic group.

6.2 Description of outcome variables in relation to hypotheses

The primary objective of this study is to assess the safety and tolerability of single ascending doses of AZD6140.

This study will also compare the pharmacokinetics (C_{\max} and AUC) and [AUC_(0-t)] if there are less than the required number of subjects with AUC estimates]) pharmacodynamics percent ADP induced platelet aggregation inhibition (%PAI) following single ascending oral doses of AZD6140 in healthy Japanese and Caucasian male and female (non-child bearing potential) subjects.

6.2.1 Demographic and baseline data

All demographic variables, including medical and surgical history, physical examination and medications taken before and during the study, as detailed in Section 4.1, will be obtained from the CRF.

6.2.2 Pharmacokinetics

Plasma concentrations of AZD6140 and its metabolite AR-C124910XX will be listed and depicted graphically as a function of time after each single dose administration. PK parameters C_{\max} , t_{\max} , $t_{1/2}$, AUC_(0-t) and AUC for AZD6140 and AR-C124910XX, and CL/F and V_z/F for AZD6140 will be estimated by non-compartmental analysis. AZD6140 and AR-C124910XX C_{\max} will be estimated as the highest measured concentration and t_{\max} will be the time to maximum concentration after single dose administration. The terminal elimination rate constant (λ_z) will be calculated by log-linear regression of the terminal portion of the concentration-time profile. The terminal elimination half-life ($t_{1/2}$) will be calculated as $0.693/\lambda_z$. AUC will be calculated using the linear trapezoidal method up to the last measurable concentration (AUC_{0-t}) and thereafter by extrapolation of the terminal elimination phase to infinity. AZD6140 CL/F will be estimated as the ratio of AZD6140 dose and AUC. The terminal phase volume of distribution, V_z/F , of AZD6140 will be estimated as the ratio of AZD6140 CL/F to λ . The PK parameters for each dose will be summarized by ethnic group - Japanese and Caucasian.

6.2.3 Pharmacodynamics

6.2.3.1 Inhibition of platelet aggregation

%PAI from pre-dose baseline will be calculated at each time using the following formula for:

$$\%PAI = 100 \times \frac{(PA_{BL} - PA_T)}{PA_{BL}}$$

where PA_T is the mean response at time 'T', and PA_{BL} is the mean response at pre-dose baseline. Percentage inhibition will be restricted to limits 0 and 100. Any data falling outside this range will be truncated to the appropriate limit.

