3. STUDY PLAN AND PROCEDURES

3.1 Overall study design

This study will be conducted at a single center in the United States. It is a randomized, double-blind placebo-controlled study to assess the safety, tolerability, pharmacokinetics and pharmacodynamics of AZD6140 when given as single ascending oral doses to healthy Japanese and Caucasian male and female (non-childbearing potential) subjects. Approximately 40 subjects will be enrolled in order to obtain 20 subjects in each ethnic group. An attempt will be made to randomize an equal number of Japanese and Caucasian female subjects in each cohort.

Subjects in each ethnic group will be divided into 2 cohorts (Cohort A and B) of 10 subjects. Within each cohort, 8 subjects will receive single ascending doses of AZD6140 on 3 occasions. Two subjects in each cohort will receive placebo on 3 occasions. Consecutive single oral doses of either AZD6140 or placebo will be separated by a washout period of at least 5 days.

The study will consist of 5 visits (a screening visit, 3 dosing/PK visits and a follow-up visit). Subjects will receive a single oral dose of AZD6140 or placebo on Day 1 of Visits 2, 3 and 4. For Cohort A dosing is scheduled to progress from 50 mg at Visit 2 to 200 mg at Visit 3 to 400 mg at Visit 4. For Cohort B dosing is scheduled to progress from 100 mg at Visit 2 to 300 mg at Visit 3 to 600 mg at Visit 4 (see Figure 1). **Prior to the subject progressing to the next higher dose level, the safety results from the previous dose level will be evaluated by**

the principal investigator and study team physician of AstraZeneca. Refer to section 3.1.7 for specific stopping criteria.

At Visits 2, 3 and 4, subjects will remain at the Clinical Research Center (CRC) for 48 hours following dosing. There will be a washout period of at least 5 days between Visits 2 and 3 and between Visits 3 and 4. A follow-up visit (Visit 5) will be scheduled 7 to 14 days following the last dose of study drug.

In order to ensure that the **lowest** dose of study drug is the first dose administered, the subjects assigned to Cohort A will be randomized and dosed prior to the subjects assigned to Cohort B. Subjects assigned to Cohort B will be randomized and dosed **after** the results of the safety evaluations from Cohort A have been assessed and a decision to progress to the next dose level has been made.

The schedule of procedures and assessments are shown in Table 1.

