Two ECGs approximately 1 minute apart will be performed at each of the following time points:
Visit 2: Day –1 at 1, 2, 3, 4, 8, 12 and 24 hours post theoretical dose.
Visits 2, 3 and 4: Day 1 at 1, 2, 3, 4, 8, 12 and 24 hours post dose.
- b **Sitting blood pressure and pulse (after sitting for 5 minutes) will be taken at the following times:**
Visit 1 (Screening)
Visits 2: Day –2, Visits 2, 3 and 4: Days –1, 1, 2, 3 and 4
Visit 5 (Follow-up)
Orthostatic blood pressure assessments (after 10 minutes supine and after 2 minutes standing) will be performed at the following times:
Visits 2, 3 and 4: 4 hours post dose
- c Blood samples for clinical chemistry, hematology and urinalysis will be obtained at the following times:
Visit 1 (Screening)
Visit 2: Day –2 and at 24 hours post dose
Visits 3 and 4: Day –1 and at 24 hours post dose
Visit 5 (Follow-up)
- d Blood samples for ALT, AST, GGT, alkaline phosphatase and total bilirubin will be obtained at the following times:
Visits 2, 3 and 4: predose
- e Randomization will occur at Visit 2 only.
- f Blood samples for pharmacokinetics will be collected at the following time points:
Visits 2, 3 and 4: Pre-dose, 0.5, 1, 2, 3, 4, 6, 8, 12, 18, 24, 36, 48, and 72 hours post dose.
- g Blood samples for platelet aggregometry will be collected at the following time points:
Visits 2, 3 and 4: pre-dose, 2, 4, 12, and 24 hours post dose.
- h Bleeding time will be assessed at the following time points:
Visit 1 (Screening)
Visits 2, 3 and 4: pre-dose, 4.5 and 24 hours post dose.
- i A single blood sample for genetic analysis will be obtained prior to dosing at Visit 2 only.
- j Visits 3 and 4 only
- k Serum pregnancy tests will be performed at Visit 1 (Screening) and Visit 5 (Follow-up).
Urine pregnancy tests will be performed at Visit 2, Day –2 and at Visits 3 and 4, Day –1.

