6.4.2 Pharmacodynamics

Percentage of platelet aggregation inhibition will be summarized using descriptive statistics over time by dose and ethnic group. Mean (or median) percentage of platelet aggregation versus time by dose and ethnic group will be presented graphically. Differences (Japanese – Caucasian) in mean (or median) percentage of platelet aggregation inhibition will be summarized by dose.

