6.4.4 PK/PD relationships

The relationship between AZD6140, AR-C124910XX, total (AZD6140 + AR-C124910XX) concentrations and %PAI will be investigated using an E_{\max} model. Data from all doses within an ethnic group will be modeled simultaneously regardless of cohort. Observed and predicted %PAI versus exposure will also be presented graphically. The E_{\max} model is a non-linear model of the following form.

$$\% PAI = \frac{E_{\max} C^{\gamma}}{C^{\gamma} + EC_{50}^{\gamma}}$$

Models with sigmoidicity factor γ equal to 1 and where γ is estimated from the data will be explored. A model including a term for ethnicity will be used to explore the effect of ethnicity on model parameters.

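### Truncating %PAI at 0 biases mean inhibition upward where the true effect is near zero; means, ethnic differences and the Emax fit should use the untruncated values

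*Protocol*

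**What the plan says.** Protocol section 6.2.3.1 gives %PAI = 100 × (PA_BL − PA_T)/PA_BL, "where PA_T is the mean response at time 'T', and PA_{BL} is the mean response at pre-dose baseline". It then limits the result: "Percentage inhibition will be restricted to limits 0 and 100. Any data falling outside this range will be truncated to the appropriate limit."

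The variable is used in two places:

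- Section 6.4.2, descriptive summaries: "Percentage of platelet aggregation inhibition will be summarized using descriptive statistics over time by dose and ethnic group". The only group contrast there is ethnic: "Differences (Japanese – Caucasian) in mean (or median) percentage of platelet aggregation inhibition will be summarized by dose".
- Section 6.4.4, the exposure-response model, where "concentrations and %PAI will be investigated using an E_{\max} model" and "Data from all doses within an ethnic group will be modeled simultaneously regardless of cohort".

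The protocol defines no untruncated %PAI, no flag for truncated values and no sensitivity analysis. Section 6.2.3.2, directly after the %PAI definition, treats its own cap differently. Bleeding times recorded as above 60 minutes are set to 60, but every summary that contains one must carry an asterisk and a footnote stating that it is biased.

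**The concern.** %PAI is negative whenever aggregation after dosing exceeds the pre-dose value. When the drug has no effect, that is ordinary noise around zero, not an impossible reading. Setting these values to 0 removes the lower half of the distribution and keeps the upper half, so the mean rises and the spread shrinks.

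Unlike a bleeding time known only to exceed 60 minutes, a negative %PAI is fully observed. The information is discarded by choice, and the reader of the report is not told.

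At stake is the description of near-baseline responses: the placebo level, and any low inhibition late after the smallest doses. Comparing platelet inhibition between Japanese and Caucasian subjects is a secondary objective (section 2.1), and the same variable carries that comparison and the Emax fit.

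**Working it through.** The protocol states no figure for %PAI variability or bias, so there is nothing to reproduce.

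**Inputs from the protocol**
- Formula and limits 0 and 100: section 6.2.3.1.
- Sampling, Table 1 footnote g: "Visits 2, 3 and 4: pre-dose, 2, 4, 12, and 24 hours post dose", that is, 4 post-dose values at each of 3 visits.
- Placebo, section 3.1: "Two subjects in each cohort will receive placebo on 3 occasions". With 2 cohorts in each of 2 ethnic groups this is 2 × 2 × 2 = 8 subjects, or 8 × 12 = 96 post-dose %PAI values if none is missing.
- Assay run in duplicate: section 4.3.1.

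**Assumptions**
- Noise in %PAI is roughly normal, with SD s between 5 and 20 points.
- True inhibition on placebo is 0.

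**Mean and SD at zero effect**

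For X ~ N(0, s), with the upper limit out of reach:
- P(X < 0) = 0.5, so about 48 of the 96 placebo values would be set to 0.
- E[max(0, X)] = s/√(2π) = 0.399 s.
- SD[max(0, X)] = s × √(1/2 − 1/(2π)) = 0.584 s.

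| Assumed SD | Reported mean (true 0) | Reported SD |
|---|---|---|
| 5 | +2.0 | 2.9 |
| 10 | +4.0 | 5.8 |
| 15 | +6.0 | 8.8 |

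A simulation of the actual ratio, with duplicate readings and a reading CV of 5%, 10% or 15%, gave %PAI SDs of 5.0, 10.1 and 15.5 and 49.8% to 50.2% negative values. Means were −0.1, −0.5 and −1.2 untruncated, against +1.9, +3.8 and +5.5 truncated. The small negative means come from the ratio form itself.

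**How fast the bias fades**

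For true mean m, the mean after flooring is m Φ(m/s) + s φ(m/s). At s = 10:
- m = 5: 5 × 0.691 + 10 × 0.352 = 6.98, bias +2.0.
- m = 10: 10 × 0.841 + 10 × 0.242 = 10.83, bias +0.8.
- m = 20: 20.08, bias +0.1.
- m = 50: no bias.

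**Ethnic difference**
- Same mean and SD in both groups: the bias cancels and 0 stays 0.
- True 10 v 0, s = 10: 10.83 − 3.99 = 6.8 instead of 10. At s = 20: 13.96 − 7.98 = 6.0.
- True 0 in both groups, SD 10 v 5: 3.99 − 1.99 = 2.0, a false difference. At SD 20 v 10 it is 4.0.
- True 60 v 50: 10.0 at s = 10 and 9.8 at s = 20, almost unchanged.

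**Emax fit**

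Simulated fits compared data with and without the floor, with the cap at 100 applied to both. Placebo was included, and concentrations were assumed either to span the EC50 or to lie mostly above it.
- SD 10: EC50 moves by at most about 2% and gamma by about 3%.
- SD 20: EC50 moves by up to about 14% and gamma by about 6% to 13% where concentrations span the EC50. The changes are smaller when most concentrations lie well above it.

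**The case against.** The strongest reply is that the floor seldom acts where it matters. The lowest dose is 50 mg. Section 1.1 reports complete inhibition at single doses of 100 to 400 mg, and more than 80% inhibition at all doses in the multiple-dose study. At those levels the floor does nothing. The pharmacodynamic analyses are secondary and descriptive, and neither the safety objective nor the sample size depends on them. All of this stands, and it limits the point to near-zero responses. It does not remove them: placebo remains. Late samples after 50 mg may also be affected, since section 1.1 gives a half-life of 6 to 13 hours and does not list 50 mg among the doses with complete inhibition. That last step is an inference.

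Section 6.4.2 also allows a median, and the floor leaves a true median at or above 0 unchanged. That stands, but the protocol does not commit to the median. In a small group, a sample median that falls below 0 would still be lifted.

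A reader might infer four stronger things that the documents do not support:

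- *That the separation of active drug from placebo is understated.* No such pharmacodynamic contrast is planned, and section 3.2 says placebo is there to evaluate safety and tolerability. What remains is a biased placebo summary.
- *That the ethnic comparison is biased in general.* Equal distributions cancel. Nothing in the protocol suggests that noise differs by ethnic group: there is one center and one assay. Even with SDs of 5 and 10 and 8 active subjects per group, the standard error of the untruncated difference is √(25/8 + 100/8) = 3.95, about twice the false 2-point difference.
- *That truncation always acts upward.* The limit at 100 pulls values down. It can act only if recorded aggregation is below zero, and the protocol does not say whether that happens.
- *That the Emax fit is seriously distorted.* At SD 10 the shift is small, and section 6.4.4 does not say whether placebo data enter the fit.

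**Conclusion.** The concern holds in limited form. Where true inhibition is near zero, the rule raises mean %PAI by about 0.40 SD and cuts the reported SD to about 0.58 of its true value. The mechanism follows from the text and the formulas. The size in points depends on an SD that the protocol does not give.

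The consequence is confined to placebo and possibly to late, low-dose samples. An ethnic difference is affected only near baseline and only if the groups differ in mean or spread. At the inhibition expected on most active doses the effect is negligible, and the Emax parameters move materially only if noise is large, around SD 20.

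This should be changed because the rule discards observed data without warning the reader and the correction is simple. It does not threaten the primary objective.

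**What to change.** In section 6.2.3.1, replace the truncation rule with a statement to this effect: means, Japanese-Caucasian differences and the Emax fit use %PAI as calculated, without truncation; values truncated to 0-100 may appear in supplementary displays only.

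If truncated summaries are kept, mark each affected one with a footnote saying that it is biased, as section 6.2.3.2 already does for bleeding times set to 60 minutes.

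The cost is one sentence in the protocol or the statistical analysis plan. No new data are needed. The downside is that some listings and plots will show negative inhibition, which a short note can explain as variation around baseline.
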